
refractory pain conditions to widespread societal use for clinical pain.

2. **Objectives** (include all primary and secondary objectives)
 1. **Primary Aim 1: Evaluate the magnitude and duration of combined dronabinol and hydromorphone to reduce pain sensitivity in a validated model of pain.** We hypothesize that the addition of a dronabinol to hydromorphone will result in a dose-dependent increase in the magnitude and duration of analgesia in patients undergoing a validated laboratory model of pain.
 2. **Primary Aim 2: Evaluate the subjective responses to combinations of dronabinol and hydromorphone to determine the subjective, euphoric effects of the combination products.** We hypothesize that dronabinol will not increase the subjective ratings of positive drug effects or other proxy measures of abuse liability, relative to hydromorphone alone.
 3. **Primary Aim 3: Evaluate the degree to which combining dronabinol with hydromorphone impacts neurocognitive performance.** We hypothesize that dronabinol may reduce neurocognitive performance at high doses, relative to hydromorphone alone, though the degree to which this may occur is unknown. This aim is critical for the advancement of potential opioid/cannabinoid combination products.
 4. **Secondary Aim 1: Evaluate whether there are sex differences on study outcomes.** We hypothesize that dronabinol enhancement of hydromorphone-analgesia will be greater among female vs. male subjects.
3. **Background** (briefly describe pre-clinical and clinical data, current experience with procedures, drug or device, and any other relevant information to justify the research).

This study will systematically evaluate whether cannabinoids can enhance the analgesic efficacy of opioids, which will advance the use of cannabinoids for the treatment of acute and/or chronic pain.

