The morning of each experimental session, the subject will receive a calorie-controlled breakfast each morning. Following breakfast, subjects will complete a baseline rating of QST and self-report measures (from which all subsequent ratings will be compared for data analysis purposes). An oral capsule containing either study drug or placebo will then be administered and hydromorphone (4mg oral in four sessions and a placebo oral dose in one session) will be administered. The time of drug administration will be selected to enable both dronabinol and hydromorphone to exert peak effects at the same time. Subjects will complete QST (see below) and self-report measures at regular intervals following study drug administration. Self-report measures will include specific opioid agonist and antagonist effects, to assess whether cannabinoids are exerting an effect on a particular category of opioid agonist symptom, and will capture whether any negative effects (e.g., nausea) occur as a function of the cannabinoid dose. Frequent collection will enable evaluation of time to peak drug effects, duration of effects, and general time course of effects and is a widely used and accepted approach in laboratory studies of drug effects. During the final assessment each day, subjects will complete a Drug vs. Money Questionnaire to indicate the dollar value they would place upon the drugs received⁹⁸. This is a well-accepted proxy measure of abuse liability. Study staff will document adverse events throughout the study and any subject who experiences a strongly unpleasant effect of the medications will be able to end participation. Any subject who is experiencing strong agonist effects at the end of the session will be provided overnight accommodation in the CRU; based on our experience we expect this to be minimal and are budgeting for 10% of sessions to have a 2nd night.

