Quantitative Sensory Testing (QST) Measures of Laboratory Evoked Pain: Subjects will complete a state-of-the-art quantitative sensory testing (QST) battery, which will comprehensively and systematically measure pain sensitivity. This approach will provide information regarding the full range of analgesic effects possible, across a wide variety of psycho-physiologically-mediated, experimentally-induced measures of pain perception. Subjects will complete a baseline QST session prior to study drug administration on each experimental session day, and will complete the pain testing battery at regular intervals during the experimental session day. Each administration of the QST battery will take 20-30 minutes. The QST battery will consist of threshold and tolerance, temporal summation, and conditioned

pain modulation (CPM) tests. The threshold responses will be conducted in randomized and counter-balanced order, and conditioned pain modulation will always occur last.

Threshold Responses will be assessed using thermal and pressure stimulation. *Thermal threshold:* All contact heat stimuli will be delivered using a peltier-element-based stimulator (Medoc, Israel). Two trials of heat pain threshold will be administered using an ascending method of limits paradigm. The thermode will gradually increase in temperature (rate of rise = .5°C/sec) from a pre-set baseline (31°C), until the subject indicates when the stimulus “first feels painful” (threshold, HPT_h) and presses a button (which terminates the procedure) indicating that the pain is intolerable (tolerance, HPT_o). *Pressure threshold:* A pressure algometer will be utilized to assess responses to pressure stimulation at a variety of anatomical sites in a randomly determined order. The pressure algometer (Somedic; Sweden) uses a rubber probe covered with 1mm polypropylene material; pressure at the site is gradually increased at a steady rate. Subjects indicate when the stimulus is first perceived as painful, which terminates the application. The algometer produces a sensation of localized pressure; technicians will place the probe of the algometer in the center of each muscle group or anatomic site when delivering the mechanical stimuli. Thirty-second inter-stimulus intervals will be maintained for all stimuli. Each trial will be averaged together to result in one HPT_h, HPT_o, and PPT_h measure.

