- **Primary Aim 1:** The primary outcome will be the area under the curve of each QST procedure, which will provide an assessment of the mean duration and magnitude of the drug effect. Primary outcomes will be tested with repeated two-factor (Drug Condition x Time) models to examine main and interaction effects for all raw data as designed. If there is large variation across subjects at the baseline timepoint, the raw data will be transformed as a change from baseline and analyzed in drug condition by time models. Statistical analyses will be conducted using multilevel analyses with an autoregressive covariance structure using SAS PROC MIXED Software¹³¹. These analyses will permit an examination for effects of drug condition and time effects associated within the course of the study. Interpretation of drug condition main effects and interactions will rely on Tukey post-hoc tests. This aim will also assess frequency of adverse events as a function of study drug.

Specific outcome variables for the QST procedures will be as follows:

- a. Heat Pain Threshold and Tolerance: HPT_h and HPT_o in °C (both in normal and capsaicin treated skin)
 - b. Pressure Pain Threshold: PPT_h in kilopascals
 - c. Thermal and Mechanical Temporal Summation: Verbal pain ratings (both in normal and capsaicin treated skin for MTS)
 - d. Conditioned Pain Modulation: The index score of CPM:PPT_h and CPM:TS (compared to baseline) for each dose
 - e. Cold Water Tolerance: Time to tolerance (compared to baseline) for each dose.
- **Primary Aim 2:** The Drug vs. Money questionnaire will be compared across dose conditions, using peak monetary rating for each dose as the primary outcome. Within-subject changes, as a function of dose, will be analyzed using a repeated measures analysis of variance (ANOVA).
 - **Primary Aim 3:** Neurocognitive tests will be compared as a function of study drug dose, using study session number (1-6) as a covariate to control for practice effects. Specific outcome measures will include:
 - a. Divided Attention Task (DAT): Accuracy with which they perform the two tasks
 - b. Digit Symbol Substitution Task (DSST): Accuracy, total number of patterns completed in allotted time
 - c. Computerized version of the Paced Auditory Serial Addition Task (PASAT): Summed of correct trials

b. Secondary outcome variables.

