Demographic and drug use characteristics, including a positive signal (defined as >20 points rating from baseline on VAS rating of Drug Effect from Session 1), that are hypothesized a priori to be associated with outcomes (e.g., Body Mass Index) will be compared across sex groups and significant differences will be included as covariates in the subsequent analyses. All analyses will be repeated and sex (male/female) will be added as a factor to the analyses.

c. Statistical plan including sample size justification and interim data analysis:

Since this will be the first study to examine the effect of cannabinoids on opioid-induced analgesia using a within-subject laboratory model of pain, there are no data available upon which a power analysis may be directly based. Therefore, we have used G-power to estimate our sample size. We estimate that a within-subject comparison using peak change from baseline as the primary outcome measure and comparing 6 medication conditions will yield power of 0.95 to detect a main effect at even a low effect size (0.2) by enrolling a sample size of 45. For each study, we are proposing to enroll 60 subjects to ensure we will have 50 study completers, and we will enroll equal quantities of men and women to examine sex-based differences in responding. This approach will result in an overall completion sample of 50 per study, with subsamples of 25 per group, which is consistent with other within-subject evaluations of drug effects. This sample size has been powered to support within-subject effects of study drug and between-subject effects of sex on study outcome measures.

d. Early stopping rules.

The safety of participants is a priority of BPRU. The largest potential risk of this study is cardiovascular in nature. This notion is based upon the results of a published study that reported an increase in heart rate and blood pressure

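### Aim 1 does not fix one primary test: the AUC outcome, the raw-data model and the sizing measure differ, the scale switches on an undefined trigger, and up to 11 QST outcomes are unranked

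*Combined protocol and SAP*

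**What the plan says.** Section 7.a, Primary Aim 1, opens with the outcome: "The primary outcome will be the area under the curve of each QST procedure". The next sentence gives the test: "Primary outcomes will be tested with repeated two-factor (Drug Condition x Time) models", applied to the raw data. The scale may then change: "If there is large variation across subjects at the baseline timepoint, the raw data will be transformed as a change from baseline". The analysis is described as multilevel, with an autoregressive covariance structure, in SAS PROC MIXED. No subject effect is written out.

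On error control the section says: "Interpretation of drug condition main effects and interactions will rely on Tukey post-hoc tests". It then lists the QST variables without ranking them. No alpha, testing order or rule for a positive Aim 1 appears.

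Section 7.c sizes the trial "using peak change from baseline as the primary outcome measure". Section 2 states the hypothesis that adding dronabinol "will result in a dose-dependent increase in the magnitude and duration of analgesia". Section 4.a plans the pre-dose data: "Subjects will complete a baseline QST session prior to study drug administration on each experimental session day".

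**The concern.** Three things are left open.

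- **Outcome and test.** One AUC per session has no time factor, so a condition-by-time model is not a model for it. The condition main effect in that model approximates the AUC comparison, but the plan does not name it as the primary test. Section 7.c uses a third measure.
- **Scale.** The move from raw to change scores depends on spread between subjects. There is no statistic or cut-off, and nothing says whether it is judged outcome by outcome. In a within-subject design that spread need not bear on which scale is better.
- **Multiplicity.** Every listed QST variable is primary, and Tukey works only within each one.

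Two analysts following the text could therefore report different primary results on whether dronabinol adds analgesia, and the switch could cost precision.

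**Working it through.** **1. The plan's own figure.** Section 7.c gives n=45 for power 0.95, effect size 0.2 and 6 conditions. With f=0.2, m=6, and assumed alpha 0.05, correlation 0.5 and sphericity: lambda = f² × n × m / (1 − rho) = 0.04 × 45 × 6 / 0.5 = 21.6, on 5 and 220 df. Power is 0.962, and 43 subjects suffice for 0.95. The 45 is thus reproduced to within two subjects, but for an omnibus test of peak change. It does not size an AUC contrast or a condition-by-time model.

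**2. Outcome count (7.a).** Heat threshold and tolerance on two skin types, 4; pressure threshold, 1; temporal summation (thermal, and mechanical on two skin types), 3; CPM, 2; cold-water tolerance, 1. Total 4 + 1 + 3 + 2 + 1 = 11. The Capsaicin paragraph of 4.a repeats only heat pain threshold and mechanical temporal summation on treated skin. If heat tolerance is not repeated there, the count is 10.

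**3. Scale, with a subject effect.** Unit: the within-subject session-to-session SD, taken as equal before and after dosing. r is the within-subject correlation of a session's pre- and post-dose values. n=50 is the completer target in 7.c. The subject effect cancels from a 10 mg versus 0 mg contrast on every scale:
- raw: SE = √(2/50) = 0.20, whatever the between-subject SD;
- change: variance ratio 2(1 − r), which is 1.4 or 0.6, so SE 0.24 at r=0.3 and 0.15 at r=0.7;
- adjusted for the session's baseline: variance ratio 1 − r², which is 0.91 or 0.51, so SE 0.19 and 0.14.

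Change beats raw only when r > 0.5. Adjustment is never worse than either: 2(1 − r) − (1 − r²) = (1 − r)² ≥ 0, and 1 − r² ≤ 1. Simulation with between-subject SD of 0.5, 1 and 4 agreed.

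The five-condition Tukey critical value on 4 × 49 = 196 df is 2.753. The difference detectable with 80% power is about (2.753 + 0.84) × SE: raw 0.72; change 0.85 or 0.56; adjusted 0.69 or 0.51.

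**4. Scale, without a subject effect.** If the only covariance is autoregressive within session, the model treats a subject's sessions as independent, so between-subject variance enters the raw contrast's SE. At between-subject SD 4 that part alone is √(2 × 16/50) = 0.80. In one assumed setting the simulated model SE rose from 0.15 to 0.80 as the SD went from 0.5 to 4, while the true sampling spread stayed near 0.16. Change scores avoid this inflation, but so does a subject effect.

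**5. False claims.** Each Tukey contrast has two-sided level 0.00645. Three dronabinol doses against 0 mg, sharing that condition, give 1.8% per outcome. For 11 independent outcomes: 1 − 0.982^11 = 0.18 (10 outcomes: 1 − 0.982^10 = 0.17). Simulation with equally correlated outcomes:

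| Outcome correlation | Any false claim | In the hypothesised direction |
|---|---|---|
| 0 | 18% | 9% |
| 0.5 | 14% | 7% |
| 0.8 | 8% | 4% |

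**6. Price of keeping all 11 primary.** At the first Holm step (0.05/11) the critical value is 3.537 at n=50 and 3.528 at n=60. The detectable raw difference rises from 0.72 to (3.537 + 0.84) × 0.20 = 0.88 at n=50, and from 0.66 to 0.80 at n=60.

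**The case against.** The strongest reply is that the trigger need not be wrong. The text says multilevel and autoregressive but never states a subject effect. On the reading in step 4, large between-subject spread does damage the raw analysis, and change scores help. That stands, so the criticism of the trigger is conditional. The missing threshold and the unstated subject effect are faults on either reading.

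It is also fair that the AUC mismatch is partly wording, since the condition main effect comes close to it. Drug-by-time speaks directly to duration, which is half of the aim, and a single AUC cannot separate magnitude from duration. The time-course model should stay.

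On multiplicity, the study looks for a signal before randomized trials and wants a broad pain battery. A single lead outcome is a trade-off, not a requirement.

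Two stronger readings are tempting and not supported:
- A reader might infer that section 4.a, where baseline ratings are those "from which all subsequent ratings will be compared for data analysis purposes", contradicts a raw-data default. Section 7.a speaks of a baseline timepoint, so baseline may be a level of Time, and the raw model then makes that comparison itself.
- A reader might infer that raw or change could be chosen after seeing results, with a much higher error rate. The written trigger looks only at baseline data, and if fixed in advance would inflate error far less.

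**Conclusion.** The point holds, as something that should be fixed. Aim 1 has three candidate primary measures and no named primary contrast. The scale switch is undefined. With a subject effect in the model it rests on the wrong quantity and can select the less precise scale (detectable difference 0.85 against 0.72 at r=0.3). Without one, it compensates for a covariance model that ignores the pairing of sessions. Either way, baseline adjustment with a stated subject effect is better.

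The 18 / 14 / 8% rates rest on an assumed 5% level, equally correlated outcomes, no true dronabinol effect on any outcome, and any one significant contrast being read as success. The documents state no such success rule, so these rates show what the silence permits and are not a property of the plan. The precision figures assume n=50 and equal within-subject SDs before and after dosing.

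One limit lies outside this point: Session 1 is always hydromorphone plus placebo, so every comparison with 0 mg assumes no session effect. Nothing proposed here removes that.

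**What to change.** In section 7.a:

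1. Delete the large-variation sentence. State a subject effect in the mixed model and always adjust for that session's pre-dose value where one is measured. Fit subject as a fixed effect, or enter the subject's mean baseline separately, so that the slope is the within-subject one; a single pooled slope with a random intercept can lose the gain when between-subject spread is large. A change-score AUC is the raw AUC minus window length × baseline, so with baseline in the model both scales give the same condition estimates. Check whether a pre-dose value exists for heat tolerance on capsaicin skin, and leave any outcome without one unadjusted.
2. Name the condition contrast on post-dose AUC over a stated window, or the equivalent time-averaged effect, as the primary test. Keep drug-by-time for duration.
3. Name one lead QST outcome, or a fixed testing order, for the formal Aim 1 claim. Keep Tukey within each outcome and report the rest as supportive.
4. Use the same measure in section 7.c.

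**Cost.** Items 1, 2 and 4 need wording and simple code, using pre-dose QST that is already planned apart from the one value to be checked. Item 3 narrows the formal claim. With a single lead outcome the false-claim rate is 1.8%. Keeping all 11 primary under Holm costs the larger detectable differences in step 6.

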
Conclusion: This will be the 1st human laboratory study to evaluate combinations of cannabinoids and opioids on a comprehensive and validated quantitative sensory testing battery, and the results of this study will identify whether a signal for this medication combination exists that should be advanced into randomized controlled trial evaluations with clinical pain populations. This study will also assess aspects that would impact drug development (abuse liability, neurocognitive impairment) and the effect of participant sex on outcomes. The ultimate goal of this research will be to determine which medication/dose combinations may exert strong analgesic effects, while minimizing abuse liability and cognitive deficits, in order to advance these medications into clinical trials for the treatment of chronic pain. This is a logical first step towards evaluating combined cannabinoid/opioids treatments for chronic pain, and will provide data necessary to support numerous evaluations of combination treatments for this population.

4. Study Procedures

- a. Study design, including the sequence and timing of study procedures (distinguish research procedures from those that are part of routine care).

Project Overview: This study will enroll 100 healthy adults, and will aim to complete 60 (30 men, 30 women) participants. Participants will conduct a within-subject evaluation of the degree to which the FDA-approved cannabinoid dronabinol (Marinol) enhances the analgesic effect of the prototypic opioid hydromorphone (Dilaudid). Subjects will complete a Screening visit to establish study eligibility and 5 experimental sessions. Experimental sessions will occur approximately once weekly and will permit subjects to admit themselves into the clinical research unit the night before the session if interested. Subjects will be provided with taxi service to and from the session. Subjects will receive a dose of hydromorphone (4mg, oral) and a double-blind oral dose of study drug or placebo the

morning of each experimental session, and will undergo QST measures of laboratory evoked pain, provide self-report ratings of drug effects, and complete a neurocognitive battery. The order of sessions will be randomized with the exception of Session 1, which will always be active hydromorphone + placebo to ensure the participant has a safe response to hydromorphone before proceeding into the remaining sessions.

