- Discomfort Intolerance Scale: A 7-item self-report measure of tolerance to distressing situations.

Session Measures:

- Clinical Opiate Withdrawal Scale: A widely used, 11-item observer-rating of opioid withdrawal symptoms.
- Vital Signs: We will assess blood pressure, pulse, respiration, and oxygen saturation.
- Pupillary Diameter: Pupil size will be assessed using an electronic Neuroptics Pupilometer
- Visual Analog Rating Scales: Participants will rate the subjective reports of drug effects items on a scale of 0 (none at all) to 100 (strongest possible), including items such as good effects, bad effects, high, withdrawal, sick, like how I feel, nausea, sedation, feel sleepy.
- Opioid Agonist/Antagonist Rating Scale: This questionnaire assesses positive and negative effects of opioids.
- Drug vs. Money Questionnaire: This questionnaire is a frequently used measure to assess relative monetary value of a drug and is being used to assess relative reinforcing effects of the drug compared to hypothetical monetary values.

Computer-based Cognitive Tests:

- Divided Attention Task (DAT): Participants simultaneously perform two different simple tasks based on visual stimuli presented on a computer screen. This task is computer based.
- Digit Symbol Substitution Task (DSST): Participants must hand type patterns presented to them on a computer screen for 90 seconds
- Paced Auditory Serial Addition Task (PASAT): Participants are provided a string of single digit numbers on the computer and must add the total of the prior to integers presented and respond by selecting the answer using the computer mouse on the screen.

Participants will also be asked to provide an optional blood sample that will be banked with the Genetic Resources Core Facility. Samples will be analyzed at a later date and governed by a separate hypothesis-driven IRB protocol. Genetic sample collection will be optional and will not impact primary study eligibility.

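### Primary Aim 2 predicts no increase over hydromorphone alone, but its only stated analysis is an omnibus ANOVA of Drug vs. Money, which cannot answer that, and no positive-effect rating has a stated comparison

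*Combined protocol and SAP*

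**What the plan says.** Section 2 (Objectives) states the Aim 2 hypothesis: "dronabinol will not increase the subjective ratings of positive drug effects or other proxy measures of abuse liability, relative to hydromorphone alone". It has a direction (no increase), one comparator (hydromorphone alone), and names positive-effect ratings before the other proxies.

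Section 7.a gives Aim 2 one outcome: "The Drug vs. Money questionnaire will be compared across dose conditions, using peak monetary rating for each dose as the primary outcome". It gives one analysis: "Within-subject changes, as a function of dose, will be analyzed using a repeated measures analysis of variance (ANOVA"). No contrast of a dronabinol dose with hydromorphone plus placebo is stated, no interval, and no rule for reading a null result. Pairwise tests appear only in the Aim 1 paragraph: "Interpretation of drug condition main effects and interactions will rely on Tukey post-hoc tests".

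Subjective ratings are collected. The Session Measures list in section 4.a has visual analog scales, "including items such as good effects, bad effects, high, withdrawal, sick, like how I feel", and an Opioid Agonist/Antagonist Rating Scale covering positive and negative opioid effects. The Experimental Sessions text refers to a "baseline rating of QST and self-report measures (from which all subsequent ratings will be compared for data analysis purposes") and gives self-report data an across-dose purpose: to see whether cannabinoids act on a category of opioid agonist symptom, and whether negative effects vary with cannabinoid dose. In the statistics section the only visual analog item is a candidate covariate in 7.b: "a positive signal (defined as >20 points rating from baseline on VAS rating of Drug Effect from Session 1").

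On order, section 4.a says: "The order of sessions will be randomized with the exception of Session 1, which will always be active hydromorphone + placebo". The dosing table in section 6.a agrees and lists five conditions, one of them double placebo.

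**The concern.** The hypothesis is one of no increase against a single comparator. The analysis tests whether any condition differs from any other. A significant result need not concern dronabinol, and a non-significant result is not evidence that nothing increased. Because the hypothesis predicts no increase, a non-significant F is the result that would appear to support it, and small or noisy data make that result more likely. The measures the hypothesis names first would reach the analysis with no pre-specified comparison to hydromorphone alone.

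The Conclusion of section 3 makes low abuse liability part of the goal of choosing combinations to take into clinical trials, so the Aim 2 reading feeds a real decision.

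**Working it through.** **The plan's own power figure.** Section 7.c claims power 0.95 with 45 subjects, 6 conditions and effect size 0.2, for a main effect on peak change from baseline. Alpha, correlation and sphericity are not stated. I assumed 0.05, 0.5 and 1, and read 0.2 as Cohen's f. Then λ = f²·N·m/(1−ρ) = 0.04 × 45 × 6 / 0.5 = 21.6, with df 5 and 220, and power is 0.962. The claim reproduces under those assumptions. With the five conditions in the dosing table, power is 0.937 at N = 45. Either way it is power to detect a difference somewhere among conditions. It is not power to exclude an increase, and it is not tied to Drug vs. Money.

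**Inputs for the checks below.** From the documents: n = 50 completers (section 7.c) and n = 60 (section 4.a, Project Overview). Assumed: normal data, compound symmetry, two-sided 5% tests, between-session correlation ρ = 0.5 with a range of 0.3 to 0.7, and every effect size. Effects are in SDs of the outcome within a single condition, so the SD of a paired difference is √(2(1−ρ)), which is 1 at ρ = 0.5. Section 7.a does not say whether double placebo enters the F test, so both readings are worked.

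1. *Double placebo included, dronabinol inert.* Means are D, D, D, D, 0. The sum of squared deviations is 4(0.2D)² + (0.8D)² = 0.8D². For D = 0.5 and n = 50, λ = 50 × 0.8 × 0.25 / 0.5 = 20, with df 4 and 196.
2. *Double placebo excluded, real increases.* Means are 0, 0.1, 0.2, 0.3. The sum of squared deviations is 0.05. For n = 50, λ = 50 × 0.05 / 0.5 = 5, with df 3 and 147.
3. *Direct paired test of one dose, true increase 0.3 SD.* Noncentrality = 0.3√n / √(2(1−ρ)), with df n−1.
4. *95% interval for one dose against hydromorphone plus placebo.* Half-width = t(0.975, n−1) × √(2(1−ρ)) / √n. At n = 50 this is 2.010 × 1 / 7.071 = 0.284.

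| Result at ρ = 0.5 (ρ = 0.3; ρ = 0.7) | n = 50 | n = 60 |
|---|---|---|
| 1. F significant, D = 0.3 | 54% (40; 79) | 63% (47; 87) |
| 1. F significant, D = 0.5 | 96% (86; 99.9) | 98% (93; 99.98) |
| 2. F non-significant | 57% (69; 34) | 49% (63; 25) |
| 3. Paired test misses 0.3 SD | 45% (58; 23) | 37% (51; 16) |
| 4. Half-width, SD | 0.28 (0.34; 0.22) | 0.26 (0.31; 0.20) |

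Rows 1 and 2 belong to alternative readings of the plan and cannot both apply.

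**Session 1.** Take 60 subjects, hydromorphone plus placebo fixed in Session 1, and the other four conditions permuted over Sessions 2–5. With categorical sessions the design matrix has 60 + 4 + 4 = 68 columns and rank 67. The Session 1 effect and the hydromorphone-plus-placebo effect are the same column, so dose versus comparator is not estimable, while dose versus dose is. With a linear session term there are 60 + 4 + 1 = 65 columns and rank 65. The contrast is then estimable, but only by carrying a slope learned in Sessions 2–5 back to Session 1. In a balanced layout the variance of the contrast grows from 2(1−ρ)/n to (2 + 2.5²/5)(1−ρ)/n, because the average gap is 2.5 sessions and each subject contributes 5 to the session sum of squares. The interval widens by √(3.25/2) = 1.27, to about 0.284 × 1.27 = 0.36 SD at n = 50.

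**The case against.** The best reply is that Aim 2 is largely estimation already. Its heading asks to evaluate subjective responses, section 6.b speaks of dronabinol increasing or decreasing drug effects, and the study is a signal-seeking laboratory experiment ahead of randomized trials. Only the hypothesis sentence predicts no increase. That stands, and it is why rewording is a sufficient remedy. It does not rescue the ANOVA, which gives no estimate against the named comparator.

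The Aim 1 Tukey tests could be extended to Aim 2. That would supply pairwise contrasts, but as difference tests, and non-significance would still not support the hypothesis.

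Four stronger readings are tempting, and the documents do not support them.

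- *The investigators will treat a non-significant F as proof of no increase.* No section says so. The plan is silent on how that result will be read.
- *Subjective ratings play no part across doses.* Section 4.a gives self-report data such a purpose. What is missing is a named Aim 2 outcome with a comparison to hydromorphone alone.
- *The fixed Session 1 makes the comparison impossible.* That holds only with categorical session effects, which no section proposes for Aim 2. Aim 3 uses session number as a covariate, and a linear term leaves the contrast estimable.
- *The aim needs a non-inferiority margin.* A margin would be needed only to claim no increase. The documents give no basis for one, and estimation needs none.

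The percentages are illustrative, because no SD is given for Drug vs. Money or any rating.

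**Conclusion.** The point holds, as two gaps in a primary aim. The stated test cannot answer the stated hypothesis under either reading of which conditions it includes. And the positive-effect ratings named first have no designated Aim 2 outcome or comparison with hydromorphone alone.

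The logical mismatch depends on no assumed number. Its size does: at 50 completers and correlation 0.5, F is significant in about 96% of trials with inert dronabinol and a 0.5 SD hydromorphone–placebo gap, or non-significant in about 57% under real increases of 0.1, 0.2 and 0.3 SD. This should be changed, but it does not invalidate the trial, because the data needed are already being collected. The Session 1 confounding affects any comparison with hydromorphone alone, including the planned ANOVA. It calls for disclosure and a sensitivity analysis, not for abandoning the comparison.

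**What to change.** - For each dronabinol dose, report the estimated difference from hydromorphone plus placebo with a 95% confidence interval. Do this for Drug vs. Money and for a small set of peak positive-effect ratings that the investigators name before unblinding, from the scales already collected.
- Base the Aim 2 conclusion on these estimates and not on the omnibus F. Reword the hypothesis as estimation, and state that a non-significant ANOVA will not be read as showing no increase.
- State that the comparator is always Session 1, so the contrast is confounded with session order: not estimable with categorical sessions, and estimable with a linear term only by extrapolation.
- Add a linear-session sensitivity analysis, and the comparison of 2.5, 5 and 10 mg within randomized Sessions 2–5 as support. The latter does not replace the comparison with hydromorphone alone.

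The cost is wording, a little more analysis, and no new data. The claim becomes weaker than no increase: at correlation 0.5 the interval is informative for estimation but wide for excluding a small rise, and wider again in the linear-session analysis.
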